Study Implementation document:

CLINICAL EVALUATION OF MYDAY LENSES

Sponsor Study Code:

Version Number:

Implementation document Date:

Sponsor Company:

Document Type:

Study Category:

[figure not shown]
Clinical Sites:

Implementation document Sponsor:	Date:
	Date:

PERSONNEL & FACILITTIES

Confidential Protocol Version 2.0: JP-MKTG-201709_02

Protocol Synopsis

Protocol / Study Number	JP-MKTG-201709_02
Title	Clinical Evaluation of CooperVision MyDay [®] Lenses
Name of Device(s) and (by USAN material)	MyDay [®] (stenfilcon A), 1-DAY ACUVUE [®] TruEye [®] (narafilcon A)
Indications for Use	Approved for use:
	stenfilcon A. (Single use daily wear)
	narafilcon A. (Single use daily wear)
	Indication for use in this study:
	3 hours of single use daily wear
Study Design	3 hours, single masked, randomized, contralateral, single use daily wear, non-dispensing study.
Purpose	The aim of this non-dispensing study is to evaluate the fitting performance of MyDay Compared it with 1-DAY ACUVUE® TruEye in a range of spherical powers.
Study Duration	The anticipated timeline for this study is as follows:
	Patient enrolment: February 2018
	Visits: V1 (Baseline), V2 (After 3 hours of lens wear/Exit visit)
Patient Population	Adapted spherical soft contact lens wearers with myopia that provide written informed consent and meet protocol entry criteria.
Sample Size	Target enrollment and completion of 40 subjects total.
Clinical Site Destination	Japan
Number of Clinical Sites	4 Sites
Patient Follow-up	Patients enrolled in this study will be followed up:
	Follow-up: 3 hours of lens wear/Exit visit
Primary Endpoints	Objective: Lens fitting characteristics, such as Lens movement, Horizontal lens centration, Vertical lens centration, Corneal coverage, Lens lag, Overall fitting performance, Investigator Fit Preference
Secondary Endpoints	Subjective: Subjective rating of wearing comfort, dryness, stinging/burning, edge awareness/lens awareness, and lens preference

TABLE OF CONTENTS

1	Intro	oduction5	
2	Stu	dy Objective6	
	2.1	Study Hypothesis	6
3	Stu	dy Design6	
4	Ethi	ics Review / Statement of Compliance6	
	4.1	Relevant Standards / Guidelines	6
	4.2	Institutional Review Board	7
	4.3	Informed Consent	7
5	Pote	ential Risks and Benefits to Human Subjects7	
6	Mat	erials and Methods8	
	6.1	Participants	8
	6.2	Study Materials	9
	6.3	Visit Schedule and Procedures1	1
7	Adv	verse Event Reporting12	
	7.1	Adverse Event Definitions1	2
	7.2	Procedures for Adverse Events1	4
	7.3	Reporting Adverse Events1	4
	7.4	Discontinuation from the Study1	5
8	Dev	rice Deficiencies15	
9	Stat	tistical Analysis15	
	9.1	Statistical analysis1	6
1	0 Data	a Quality Assurance16	
	10.1	Study monitoring1	6
	10.2	Record keeping1	6
	10.3	Record retention1	7
	10.4	Data Entry / Data Management1	7
	10.5	Confidentiality1	7
	10.6	Publication1	7
1'	1 Stu	dy Costs17	

DOCUMENT CHANGE HISTORY

1 Introduction

Cooper Vision Inc. is interesting in evaluating the fitting characteristics of its MyDay lenses in an Japanese population.

2 Study Objective

This is a feasibility study to evaluate the fitting performance of MyDay lens (Test) against TruEye (Control) over 3 hour of lens wear in a Japanese population.

The key variables of interest is:

• Lens fit performance

Other variables of interest are:

- Subjective comfort, dryness, stinging/burning, edge awareness/lens awareness and preference

2.1 Study Hypothesis

The study primary hypothesis is that there will be no differences between the Test and Control lenses in term of fitting characteristics.

3 Study Design

This will be a non-dispensing, randomized, contralateral study comparing a test lens against an appropriate control lens. Each subject will be randomized to wear the test lens in one eye and the control lens in the other eye. It is anticipated that this study will involve up to 2 visits.

4 Ethics Review / Statement of Compliance

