7.3 Visit Schedule and Procedures

7.3.1 Visit 1: Baseline Visit

Procedures to be Performed

The following evaluations will be performed to assess eligibility according to the Inclusion and Exclusion Criteria at the baseline visit only:

- The study lenses will be fitted according to the randomization table.
- Subjective ratings on insertion will be recorded according to the CVJ defined 0-10 scales. Lens preference will be recorded.
- The study pair of contact lenses will be allowed to settle for 5 minutes.
- The subject will be asked to score their subjective response according to the CVJ defined 0-10 scales. Lens preference will be recorded.
- Lens fit will then be assessed and graded according to the CVJ defined Grading scales.
- The subject will be discharged and asked to return for a follow-up visit after 3 hours.

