10.1 Statistical analysis

Summary statistics will be produced (e.g. mean, standard deviation).

and subjective scores between study lens types. $\chi 2$ test will be used to compare the fitting performance between study lens types. The critical alpha level for statistical significance will be set at p ≤ 0.05 , with adjustment for multiple comparisons.

All participants who were evaluated will be used in the analysis. In the event of missing data, individual data points will be excluded in the analysis and not extrapolated from the collected data.

11 Data Quality Assurance

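### The primary hypothesis is that the lenses do not differ in fit, but the visible fit analysis is a difference test with no margin or named interval, so it can reject that hypothesis but not support it

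*Combined protocol and SAP*

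**What the plan says.** Section 2.1 (Study Hypothesis) states: "The study primary hypothesis is that there will be no differences between the Test and Control lenses in term of fitting characteristics". It gives no alternative hypothesis and no margin.

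Section 3 (Study Design) makes the comparison contralateral: "Each subject will be randomized to wear the test lens in one eye and the control lens in the other eye". Each subject therefore supplies one Test eye and one Control eye.

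The synopsis lists seven fit characteristics as primary endpoints, introduced by 'such as', and targets 40 completed subjects. Section 7.3.1 describes the scoring: "Lens fit will then be assessed and graded according to the CVJ defined Grading scales". The scale itself is not in the text. Table 2 in section 7.3.3 marks lens fit assessment at both visits.

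Section 10.1 plans summary statistics, with mean and standard deviation given as examples. For fit, a χ2 "test will be used to compare the fitting performance between study lens types", at p ≤ 0.05 "with adjustment for multiple comparisons". One sentence survives only as "and subjective scores between study lens types"; its beginning is missing from the supplied text.

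Section 2 calls the trial a feasibility study.

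**The concern.** A difference test takes equality as its starting point and can only produce evidence against it. When equality is also what the study hypothesises, the expected result is a non-significant p-value. That result may mean the lenses fit alike, or that 40 subjects were too few to show how they differ. Without a margin or an interval the reader cannot tell which.

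The design could do better. Each subject wears both lenses, so the trial can estimate the within-subject difference in fit directly. The visible plan does not commit to reporting that difference with its uncertainty. What is at stake is whether the trial can answer its own primary question, and how large a deficit in fit remains possible when nothing significant is found.

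**Working it through.** **The plan's own figure.** The sample size of 40 cannot be reproduced: the documents give no power, effect size, variability, discordance or margin. What can be shown is the precision that 40 pairs give.

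**Inputs.** n = 40 pairs (synopsis; one eye per lens, section 3), all complete. Two-sided 95% intervals, z = 1.96. Yes/no scoring of fit and the proportion d of discordant pairs (acceptable with one lens only) are assumptions; d is varied from 0 to 30%.

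**Yes/no fit, no observed difference.** When discordant pairs split evenly, the paired score (Tango) interval is symmetric about zero, with half-width √(u² + d·u(1−u)), where u = z²/(n + z²) = 3.84/43.84 = 0.0876. Then u² = 0.00768 and u(1−u) = 0.0799.

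| Discordant pairs | Half-width | Points |
|---|---|---|
| 0% (0 v 0) | √0.00768 | ±8.8 |
| 10% (2 v 2) | √(0.00768 + 0.00799) | ±12.5 |
| 20% (4 v 4) | √(0.00768 + 0.01599) | ±15.4 |
| 30% (6 v 6) | √(0.00768 + 0.02398) | ±17.8 |

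**Numeric fit score.** Half-width = t(0.975, 39)/√40 = 2.023/6.325 = 0.32 SD of the paired difference.

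**Investigator Fit Preference.** An even 20/40 split, assuming no ties, has a Wilson 95% interval of 35% to 65%.

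**Would equivalence be a better aim?** With no margin in the documents this can only be bracketed. For two one-sided tests at 0.05, 80% power and a true difference of zero, pairs needed = d(1.645 + 1.282)²/m², with (1.645 + 1.282)² ≈ 8.56. Assuming a margin m of 20 points and d = 10%: 8.56 × 0.1/0.04 = 21.4, so 22 pairs. With m = 10 points and d = 30%: 8.56 × 0.3/0.01 ≈ 257 pairs. Forty lies inside that range, so it cannot be called adequate or inadequate.

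**The case against.** The strongest reply is that section 2.1 merely states a conventional null and section 10.1 names a test of it. The stated aim, to evaluate fit against the control in a feasibility study, is neutral. A reader might infer that the sponsor means to report non-significance as similarity or equivalence. No section says so, and that reading should not be pressed. For the same reason the stricter alpha, which makes non-significance easier to reach on each endpoint, would be a defect only if non-significance were the success criterion, which is not stated. Even read as a plain null, though, the sentence is the study's only primary hypothesis, and the visible analysis cannot support it.

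The second reply is that section 10.1 is incomplete in the supplied text. The broken sentence begins with 'and', so something came before the subjective scores, and the summary statistics are examples, not a full list. A reader might infer that the plan contains no interval for fit at all. The documents show only that none is named in what survives. This stands, and it narrows the fix.

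Third, a reader might infer that the named test would miss a particular deficit. That depends on the marginal rates and on the form of χ2 test. With an ordinary uncorrected χ2, two results that are both five eyes apart (5/40 = 12.5 points) fall on opposite sides of 0.05:
- 38/40 v 33/40: pooled rate 71/80 = 0.8875; χ2 = 0.125²/(0.8875 × 0.1125 × 2/40) = 3.13; p = 0.077.
- 39/40 v 34/40: pooled rate 73/80 = 0.9125; χ2 = 0.125²/(0.9125 × 0.0875 × 2/40) = 3.91; p = 0.048.

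No general statement about what the test would miss is therefore made here.

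Finally, no clinically relevant difference in fit is given, so the interval widths cannot be called too wide. They show only what a statement of no difference would leave unsaid.

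**Conclusion.** The point holds in limited form. The visible plan can reject its primary hypothesis but cannot support it, because it has neither a margin nor a named interval for fit. With 40 complete pairs and no observed difference, differences of 8.8 to 17.8 points in either direction would remain compatible with the data, assuming yes/no scoring and 0 to 30% discordant pairs. For a numeric score the figure is 0.32 SD of the paired difference. Missing observations, which section 10.1 excludes, would reduce the number of pairs and generally widen these intervals.

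The mismatch between hypothesis and visible analysis needs no numerical assumption; only the illustration of its size does. Severity is minor to should-fix, given the feasibility label, the lost text and the absence of any stated similarity claim.

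**What to change.** In section 2.1, replace the hypothesis with:

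> The primary objective is to estimate the within-subject difference in each fitting characteristic between the Test and Control lenses.

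In section 10.1, add:

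> For each fit endpoint and visit, the paired Test-minus-Control difference will be reported with a two-sided 95% CI (paired score interval for yes/no outcomes; mean difference for numeric scores; for ordered categories, the paired difference in the proportion at or above a prespecified grade). For Investigator Fit Preference, the proportion preferring each lens will be reported with its 95% CI. Any test of difference in fit will use a method that respects the pairing. A non-significant result will not be reported as no difference or similarity. The CIs are unadjusted and descriptive; claims of a difference rest on the multiplicity-adjusted test.

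If the lost text of 10.1 already gives a paired interval for fit, only the 2.1 wording, the paired-test sentence and the reporting sentences are needed. The sponsor must choose the wording that matches its grading scale and, for ordered categories, fix the grade in advance.

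The cost is wording and a paired analysis, with no added subjects or measurements. The conclusion becomes an estimate with its uncertainty, which is less favourable than a statement of no difference. Seven listed endpoints at two visits give 14 unadjusted intervals, of which about 14 × 0.05 = 0.7 would exclude no difference by chance if the lenses were identical. That is why claims of a difference stay with the adjusted test.

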4.1 Relevant Standards / Guidelines

This implementation document has been developed in accordance with the following:

Confidential

- ISO 14155 Clinical Investigation of Medical Devices for Human Subjects, Parts 1 & 2
- ICH Harmonized Tripartite Guideline for Good Clinical Practice
- Declaration of Helsinki

4.2 Institutional Review Board

This study will be conducted in accordance with Institutional Review Board regulations (U.S. 21CFR Part 56.103) or applicable IEC regulations. Copies of all IRB/IEC correspondence with the investigator/sponsor will be kept on file.

4.3 Informed Consent

Informed consent shall be obtained in writing from the subject and the process shall be documented before any procedure specific to the clinical investigation is carried out.

5 Clinical Trial Registration

- 1. This study will be registered in www.ClinicalTrials.gov.
- 2. Prior to the implementation of the study, the contents of the study protocol will be registered with masking the key words and numbers to protect the company confidentiality in the publication database set up by the Japan Pharmaceutical Information Center and will be updated suitably according to the change and progress.

Results of this study will be released with masking the key words and numbers to protect the company confidentiality only in the publication database set up by Japan Pharmaceutical Information Center after taking necessary measures for the protection of the human rights of study subjects and related parties or the rights and profits of researchers, etc. and related parties, without delay after the completion of the study.

6 Potential Risks and Benefits to Human Subjects

There might not be direct benefits to the subjects in this study. However, participation in a study may contribute to scientific research information that may be used in the development of new contact lens products. In addition, subjects will receive an examination of the front part of their

Confidential

eyes and may have the opportunity to try a different type of soft contact lenses and/or different lens care products at no cost to them.

The investigational contact lenses used in this study are intended for daily wear (NOT extended wear) with usage of up to 12 hours only, in contrast to the average wearing time of 10-16 hours for daily wear lenses. In addition, this study is a non-dispensing study, meaning the lenses are not dispensed to subjects to take home and lens wear will be monitored closely by the investigators. This study is considered to be a non-significant risk study based on United State Food and Drug administration (FDA) and International Standards Organization (ISO) guidelines due to the daily wear nature of the study.

Complications that may occur during the wearing of contact lenses include discomfort, dryness, aching or itching eyes, excessive tearing, discharge, hyperemia and variable or blurred vision. More serious risks may include photophobia, iritis, corneal edema or eye infection. Although contact lens-related infections are very infrequent, the possibility does exist. The incidence of infection due to day-wear soft lenses is 0.035%. Almost always an infection will occur only in one eye. This risk is assumed by 35-million Americans who currently wear contact lenses.

The lenses being used may not have the exact prescription power needed by the subject. The prescription closed to the available SKUs without the over minus correction will be made for each eye. This may require that subjects wear their spectacle correction over the study lenses in order to see well at distance. In this case, it is possible that subjects may experience "eye strain" when focusing through this extra power which may cause headaches. Routine clinical procedures including auto-refraction, auto-keratometry, visual acuity, anterior ocular health assessment, and contact lens fitting will be used.

7 Materials and Methods

7.1 Participants

Approximately 40 subjects will be enrolled for this study. All subjects will be Japanese. Each subject will be given a unique ID number. Additionally, all subjects must meet the study inclusion and exclusion criteria listed below.

Confidential

Inclusion criteria

A person is eligible for inclusion in the study if he/she:

- Is Japanese
- Has had a self-reported oculo-visual examination in the last two years.
- Is at least 18 years of age and has full legal capacity to volunteer.
- Has read and understood the informed consent letter.
- Is willing and able to follow instructions and maintain the appointment schedule.
- Is correctable to a visual acuity of 20/40 or better (in each eye) with their habitual vision correction or 20/20 best-corrected.
- Currently wears soft contact lenses.
- Has clear corneas and no active ocular disease.

Exclusion Criteria

A person will be excluded from the study if he/she:

- Has never worn contact lenses before.
- Has any systemic disease affecting ocular health.
- Is using any systemic or topical medications that will affect ocular health.
- Has any ocular pathology or severe insufficiency of lacrimal secretion (moderate to severe dry eyes) that would affect the wearing of contact lenses.
- Has persistent, clinically significant corneal or conjunctival staining using sodium fluorescein dye.
- Has any clinically significant lid or conjunctival abnormalities, active neovascularization or any central corneal scars.
- Is aphakic.
- Has undergone corneal refractive surgery.
- Is participating in any other type of eye related clinical or research study.

7.2 Study Materials

7.2.1 Contact lens

Subjects will be randomized to receive either the Test or Control lens as a matched pair at each visit per a predetermined randomization schedule. The Test lenses used in this study will be

Confidential

provided by the Sponsor. The Control lenses will be sourced by the site. Details of the contact lenses are shown in Table 1.

	MyDay (Test)	TruEye (Control)
Material	stenfilcon A	narafilcon A

7.2.2 Contact Lens care

No contact lens care is required for this study as lenses are to be worn for a single day only.

7.2.3 Storage of Lenses and Lens Care Solutions

The study materials must be stored in a secured area. All lenses and lens care solutions should be stored at controlled room temperature (59-86°F).

7.2.4 Clinical Supply Inventory

The investigator must keep an accurate accounting of the study product during the study. A detailed inventory must be completed for study supplies. The study supplies are to be used in accordance with the implementation document by subjects who are under the direct supervision of an investigator.

7.2.5 Disposal of Consumables

This study dispenses consumables (lenses) to participants for use during the study. Study lenses worn by participants will be discarded at the each site.

7.2.6 Masking and Control of Study Materials

The contact lenses coding will be masked to subject.

7.2.7 Ordering and Accountability of Study Materials

The test lenses and the control lenses will be provided by the sponsor.

The investigator must complete an accurate accounting of the study product at the completion of the study. A detailed inventory must be completed for study supplies. All unused materials will be

returned to the Sponsor at the end of the study unless the investigator is otherwise directed by the study Sponsor.

7.3 Visit Schedule and Procedures

7.3.1 Visit 1: Baseline Visit

Procedures to be Performed

The following evaluations will be performed to assess eligibility according to the Inclusion and Exclusion Criteria at the baseline visit only:

- The study lenses will be fitted according to the randomization table.
- Subjective ratings on insertion will be recorded according to the CVJ defined 0-10 scales. Lens preference will be recorded.
- The study pair of contact lenses will be allowed to settle for 5 minutes.
- The subject will be asked to score their subjective response according to the CVJ defined 0-10 scales. Lens preference will be recorded.
- Lens fit will then be assessed and graded according to the CVJ defined Grading scales.
- The subject will be discharged and asked to return for a follow-up visit after 3 hours.

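### At Visit 1 the subject's ratings and lens preference are recorded twice before fit is graded, and nothing readable in the plan keeps them from the fit grader

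*Combined protocol and SAP*

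**What the plan says.** All references are to the combined protocol and SAP.

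- **Order at Visit 1 (section 7.3.1).** After the lenses are fitted, "Subjective ratings on insertion will be recorded according to the CVJ defined 0-10 scales. Lens preference will be recorded". The lenses settle for 5 minutes, and then "The subject will be asked to score their subjective response according to the CVJ defined 0-10 scales. Lens preference will be recorded". The next step is "Lens fit will then be assessed and graded according to the CVJ defined Grading scales".
- **Primary endpoints (labelled as objective in the Protocol Synopsis).** The list is "Lens fitting characteristics, such as Lens movement, Horizontal lens centration, Vertical lens centration, Corneal coverage, Lens lag, Overall fitting performance, Investigator Fit Preference", as given there.
- **Secondary endpoints (labelled as subjective in the Protocol Synopsis).** The list is "Subjective rating of wearing comfort, dryness, stinging/burning, edge awareness/lens awareness, and lens preference", as given there.
- **Design and masking.** The synopsis describes a "3 hours, single masked, randomized, contralateral, single use daily wear, non-dispensing study". Section 3 randomizes the test lens to one eye and the control lens to the other. Section 7.2.6 says "The contact lenses coding will be masked to subject" and describes no masking of anyone else.
- **Visit 2 (section 7.3.2).** Subjective scoring and lens preference come first. Two bullets are blank in the available text, so the position of the fit assessment cannot be read. Table 2 shows that one takes place.

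**The concern.** The synopsis treats fit as the objective primary outcome and comfort and preference as the subjective secondary one, and the hypothesis in section 2.1 concerns fit alone. That separation holds only if the fit judgement is made without knowledge of the subject's answers.

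In a contralateral study a preference for one lens is a preference for one eye, and the grader then compares the same two eyes. Items that call for an overall or comparative judgement, such as "Overall fitting performance, Investigator Fit Preference", look the most open to a cue of this kind. If the grader follows it, a difference in comfort could be reported as a difference in fit. The two sets of endpoints would also appear to support each other partly because one informed the other.

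This route differs from knowledge of the lens brand. A grader who did not know which lens was which could still be told which eye feels better.

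**Working it through.** The plan gives no figure on this point, so there is none to reproduce. The check is a comparison of the relevant sections, followed by an illustration of scale.

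**Step 1: order.** The sequence in section 7.3.1 is ratings and preference, settling, ratings and preference, fit grading. The subject's view is therefore on record twice before grading, the second time in the step immediately before it.

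**Step 2: does the preference identify an eye?** Yes. Section 3 puts one lens type in each eye of every subject.

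**Step 3: is the grader shielded?** The synopsis (single masked) and section 7.2.6 mask the subject to lens coding. No readable section names a separate fit grader, says who records the subject's answers, or withholds them from the grader. Section 11.2 refers to Case Report Forms, but these are not part of the document, so their layout and handling cannot be checked.

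**Step 4: which items are exposed at this step?** The fit grades are, by section 7.3.1. Investigator Fit Preference appears only in the synopsis, and 7.3.1 does not say when it is recorded, so its exposure here is conditional.

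**Step 5: illustrative scale.** Inputs:

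- From the synopsis: 40 subjects.
- Assumed, not from the documents: no true fit difference; a forced choice, so that an uninfluenced investigator splits 50/50; 65% of subjects preferring one lens; and a fraction w of subjects in whom the investigator copies the subject's preference.

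Investigator preference share = 0.65w + 0.5(1 − w) = 0.5 + 0.15w.

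Investigator–subject agreement = w + 0.5(1 − w) = 0.5 + 0.5w.

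| w | Share for the preferred lens | Shift among 40 subjects | Agreement |
|---|---|---|---|
| 0 | 0.500 | 0 | 0.50 |
| 0.2 | 0.530 | 40 × 0.03 = 1.2 | 0.60 |
| 0.5 | 0.575 | 40 × 0.075 = 3.0 | 0.75 |

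**Step 6: would this produce a false fit difference?** As an illustration, take an exact two-sided binomial test of the investigator's preference in 40 subjects, rejecting at 13 or fewer or at 27 or more. Section 10.1 names a chi-square test, so this is not the planned analysis. The rejection probability is 3.8% at a share of 50%, 5.3% at 53% and 13.2% at 57.5%, before the multiplicity adjustment that section 10.1 calls for.

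**The case against.** The strongest reply is that exposure is inferred. Section 7.3.1 is written in the passive throughout. It does not say that the grader asks for, hears or records the subject's answers, and subjects may already complete a form that the grader never sees. This stands. A reader might infer from the order that the grader knows the preference, or that the fit grades are contaminated. The documents support only that they could be.

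Four further objections also carry weight:

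- **Magnitude.** Both 65% and w are assumed, and the illustration covers a single item. Nothing is quantified for movement, centration, coverage, lag or overall fit, and the grading scales are not shown. On the assumed values the preference share moves by at most 3 of 40 subjects. The larger agreement figures describe a comparison that is neither a listed endpoint nor a planned analysis.
- **Visit 2.** A reader might extend the finding to the 3-hour visit. The text there is incomplete, so no ordering error can be alleged. The plan also does not say which visit's fit grade is primary, and section 2 speaks of performance over 3 hours of wear, so the 5-minute grade may not be the decisive one.
- **Direction.** Lenses are randomized to eyes and subjects are masked, so the cue favours one lens only if comfort really differs between lenses.
- **Priority.** No masking of the grader to lens identity is described. That is a more direct route to biased fit grades, and withholding the subject's form does not close it.

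The order itself is not the defect. Grading fit first could disturb the subject's comfort ratings. What survives the objections is narrower: the plan leaves this route open, and it can be closed at very little cost.

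**Conclusion.** The point holds in limited form. At Visit 1 the subject's ratings and preference precede fit grading, and no readable section keeps them from the grader. In this contralateral design they could cue judgement-type primary items and carry a real comfort difference into the fit result. That conclusion rests on the order in 7.3.1, the one-lens-per-eye allocation, and the absence of any readable safeguard. For Investigator Fit Preference it also rests on that item being recorded at this step.

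The size of any bias cannot be estimated from the documents. The 53% and 57.5% shares show only what assumed values would imply: a modest shift in the preference share, and no large rise in false fit differences unless the grader copies the subject often. For a 3-hour feasibility study this is a worthwhile low-cost safeguard and not a threat to the study's validity. It is best put in place before enrolment, because w is not observed and an analysis could not reliably remove the influence afterwards.

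**What to change.** Keep the order of assessments. Add a sentence to section 7.3.1, and to section 7.3.2 wherever ratings precede fit grading, along these lines: the subject completes the ratings and lens preference on a separate form, and the fit grader does not see it until the fit grades and Investigator Fit Preference have been entered and signed. State in the same place that complaints needing attention still go to the investigator at once.

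It would also help to say in 7.3.1 when Investigator Fit Preference is recorded, because its exposure depends on that.

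The cost is one protocol sentence and one separate CRF page, with no extra staff, visits or procedures. The downside is slightly less convenient form handling. Masking of the grader to lens identity needs its own decision and is not resolved by this change.
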